The intervention group will be exposed to the film on two occasions. Access to the film is imbedded within the intervention group's online questionnaires and the film is first made available immediately following completion of baseline background and PROM data collection. Further exposure occurs at the data collection time point prior to the initial physiotherapy consultation. The time from baseline to the initial physiotherapy consultation will vary for each participating patient depending on clinical prioritisation and the accessibility of initial consultations at the participating physiotherapy departments. The film is hosted on RÖ's Quick channel, viewable on any electronic device and is exclusively available to the intervention group via the questionnaires. In order to reduce the risk of contamination bias the film is not shareable or available via online searching.

All participating physiotherapists will provide initial consultations to patients in both the intervention and control groups. For the intervention group the initial physiotherapy consultations will take place as usual with the addition of the discussion around the film and questionnaires. Any tailoring of the physiotherapists' responses to the patients' answers will occur according to the preferences and skills of each individual physiotherapist. The physiotherapists will not have access to the results of the questionnaires completed by the patients prior to the initial consultation.

Why

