Self-reported global rating of change will be measured using a single item Global rating of change scale (GRoCs) scored on an eleven-point scale. The eleven-point scale is scored from minus five to plus five, anchored by the terms very much worse (minus 5), unchanged (0) and completely recovered (plus 5) in accordance with the recommendation made by Kamper et al. (2009). The score is based on the period from when the patient first contacted the physiotherapy department to the GRoCs data collection time points. GRoCs are widely used in MSKP research and despite being vulnerable to recall bias, have good face and construct validity, test-retest reliability and good sensitivity to change (Kamper et al., 2009). GRoCs have been recommended as a core outcome measure for MSKP research as they are sensitive to patients' priorities and are flexible to diverse conditions or pain sites, all factors pertinent to this study (Kamper et al., 2009). The GRoCs is also included in this study as an anchor for calculation of study specific MCIDs and analysis of the ÖMPSQ's predictive ability.

- *Physical activity levels*

Levels of physical activity will be collected via three self-report screening questions developed for the Swedish national board of health and welfare (Kallings, 2014; Olsson et al., 2016). These three questions ask the patients how many minutes in the last week they have performed exercise that makes them breathless, how many minutes they have been otherwise

physically active besides exercise, for example doing housework or gardening, and how many hours they usually sit during a day (not including sleeping). From these questions it can also be calculated if patients attain a threshold of at least 150 mins per week of moderate intensity physical activity. These questions are included as a secondary outcome measure as the PainSMART-strategy aims to impart the message that maintaining physical activity, even whilst in pain, is important (Caneiro et al., 2022).

- *Self-reported analgesic use*

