All participant data will be handled and processed by the research team responsible for the study. All participants will be pseudonymised via the use of a code-key system. All patient participant questionnaire data will be collected electronically via the Webropol system. Webropol data is hosted on a secure server within RÖ. Non-responders to the questionnaires will receive SMS and telephone reminders in order to reduce dropouts and missing data. At the conclusion of the study all Webropol data will be transferred to Linköping University's secure server for analysis. In addition, physiotherapist background data will be collected via Webropol questionnaires and physiotherapy PREMs data via secure messages within RÖ's and RJL's electronic journal system. Reminders will be sent to the physiotherapists via the electronic journal system regarding the evaluation of the initial physiotherapy consultations. Physiotherapist initial consultation evaluation data will be stored pseudonymised via code-key on an excel-file and transferred to Linköping University's server for analysis. The code-keys for patients and physiotherapists will be stored separately from the online data. Dictaphones will be used to record the initial physiotherapy consultations in the qualitative phase of the RCT. The audio files will be uploaded from the Dictaphones to Linköping University's secure NextCloud service. Patients and physiotherapists will be anonymised during analysis of the audio recordings and transcripts of the recordings. Data management will comply with the European Union's General Data Protection Regulation (GDPR). The information provided to potential participants will clearly state that their data will be handled and stored securely whilst analysis and reporting of results will be pseudonymised and at group level so that it is not possible to identify individuals. Secure data storage will continue throughout the study and for a minimum of ten years after its conclusion according to current Swedish legislation for research data (IMY, 2023). Only the research team will have access to the data in the study and will be responsible for data processing together with statistical support staff at Linköping University.

Statistical methods

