on generalisability (Mercieca-Bebber et al., 2018). All outcome data will be compared based on the ITT principle. This means that all patients that have been randomised remain in the analysis based on their group allocation. In the event of substantial missing data, evaluation of the mechanisms for missing data will be used (Enders, 2011). Missing data will otherwise be handled under the missing at random assumption (Enders, 2011). Multiple Imputation or Maximum Likelihood estimation will be used assuming that missing data is conditional on variables included in the model. Imputation method considering missing at random or not missing at random will be used in the ITT analysis. Patients who cancel their initial physiotherapy consultation will be excluded from the PREM analysis but will remain in the study for PROM and healthcare register data analyses.

Study monitoring and harms

There will be no data monitoring committee since the study is independent from the sponsor and the intervention is implemented as an adjunct to usual physiotherapy management with low risk for unexpected adverse events. The PROMs included in the study are sensitive to worsening in the patients' condition. An internal pilot interim analysis was planned and conducted (February 29th, 2024) after approximately 50% of the initially planned sample (n = 229) had consented to the study and reported outcomes at time point two (72-24 hours prior to the initial physiotherapy consultation) and three (24 hours post the initial physiotherapy consultation). This interim analysis enabled evaluation of the viability of the a-priori sample size calculation and the recruitment frequency. The analysis utilised linear mixed models to investigate between group differences (effect size) for change from baseline to time points two and three for outcome. The significance level for the interim analysis was p=0.05. After interim sample size calculation, the sample size was adjusted slightly to take loss to follow-up into account. The sample size calculation is described under the protocol heading sample size. The trial would have been stopped if the internal pilot interim analysis could not be performed due to not attaining 50% of the sample size at Time point two and three within six months. No further interim analyses are planned.

Ancillary and post-trial care

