Physical activity in the past week will be measured using three screening questions developed for the Swedish national board of health and welfare.

1. Self-reported physical activity in the past week regarding moderate to intensive exercise (minutes)
2. Other physical activity beside exercise (minutes)
3. Sitting time (minutes during a regular day)
 - Time Frame: collected at baseline, 24 -72 hours prior to the initial physiotherapy consultation, 24 hours post initial physiotherapy consultation and at three months post-baseline.
 - Calculation to derive outcome:
 - Within and between group mean change in the scores over time from baseline to follow-up three months post-baseline (all time points). Scores on question regarding “Moderate to intensive exercise” and “Other physical activity beside exercise” will also be converted to activity minutes per week < 150min/w or \geq 150min/w.

-Global rating of change

Global rating of change will be measured using a single item Global Rating of Change Scale (GRoCs) scored on an 11-point scale from minus five to plus five, anchored by the terms very much worse (minus five), unchanged (zero) and completely recovered (plus five). The score is based on the period from when the patient first contacted the physiotherapy department to initiate triage until the data collection points for the GRoCs.

- Time Frame: collected at 24 -72 hours prior to the initial physiotherapy consultation, 24 hours post initial physiotherapy consultation and at three months post-baseline.
- Calculation to derive outcome:
 - The score will be dichotomized into improved (1-5) and unchanged/worse (-5-0).

-Analgesic medication use

Self-reported analgesic medication use (type and consumption) for the presenting MSKP complaint will be established via two questions. The first question establishes self-reported consumption of analgesics with the answer alternatives: Yes, on a regular basis; Yes, sometimes; or No. The second question establishes the type of analgesics taken for MSKP and is ranked according to the analgesics ladder recommendations from the Östergötland health care region pharmaceutical committee (2024) (1. Paracetamol, 2. NSAID, 3. Opioids/gabapentinoids/Tricyclic antidepressants/Serotonin-norepinephrine reuptake inhibitors).

- Time Frame: collected at baseline, 24 -72 hours prior to the initial physiotherapy consultation, 24 hours post initial physiotherapy consultation and at three months post-baseline.

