- Intervention group:
 - Responders: patients attaining within group mean change equal to and above the study specific threshold for MCID.
 - Non-responders: patients attaining within group mean change below the study specific threshold for MCID.
- Control group:
 - Responders: patients attaining within group mean change equal to and above the study specific threshold for MCID.
 - Non-responders : patients attaining within group mean change below the study specific threshold for MCID.

The group comparison refers to the difference in responder rates between the intervention and the control group using Chi-square test for independence.

Mediation analysis

The planned mediation analysis of the PainSMART-study will help analyse the causal mechanisms of the PainSMART-strategy. If the PainSMART-strategy is found to be effective, the causal mediation analysis will help explain how the strategy works. Conversely, if the strategy is not found to be effective, the causal mediation analysis will help identify where the hypothesised mechanisms broke down.

Primary mediation objective

The primary objective is to confirm if improvement in hypothesised mediators, MSKP illness perceptions and reassurance of the benign nature of MSKP, mediate the effect of the PainSMART-strategy on pain intensity and pain self-efficacy.

Rationale for the hypothesised mediators

MSKP illness perceptions and level of reassurance as to the benign nature of MSKP are hypothesized, based on an integration of the CSM and concept of self-efficacy, to be potential mediators of the effect of the PainSMART-strategy on pain intensity as well as other secondary outcomes. The integrated model also hypothesizes pain self-efficacy to be a mediator in a series of mediators of the PainSMART-strategy's effects. The theoretical rationale underlying the hypothesised mediators in the PainSMART-strategy are explained in full in the trial protocol.

Outcomes

Primary outcomes are average pain intensity in the previous 24 hours measured with a 11-point NRS and pain self-efficacy measured with PSEQ-10. Hypothesised mediators are MSKP illness perceptions measured with the BIPQ and level of reassurance as to the benign nature of MSKP measured with a 11-point NRS.

Data collection

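### The protocol points to PROMs that can register worsening, but no planned analysis counts the patients who got worse

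*Protocol*

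**What the plan says.** The protocol section on study monitoring and harms opens: "There will be no data monitoring committee since the study is independent from the sponsor". It adds that the intervention is a low-risk adjunct to usual care. The next sentence begins: "The PROMs included in the study are sensitive to worsening". The text of neither document describes recording of adverse events, a threshold for deterioration, review of scores during follow-up or a harm-based stopping rule. The section on ancillary care says only that usual care stays open if an unexpected event occurs.

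The SAP analyses the PROMs in three ways:

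- **Continuous scores.** The primary and secondary outcome analyses compare group mean change in mixed models.
- **GRoC.** It is collected on a scale that runs down to minus five (very much worse), but the SAP then says: "The score will be dichotomized into improved (1-5) and unchanged/worse (-5-0").
- **Responder analysis.** Each arm is split in two at the study-specific MCID, with the lower group defined as "Non-responders: patients attaining within group mean change below the study specific threshold for MCID". I read this as each patient's own change.

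On access to scores, the protocol says under its heading on where and how the intervention is given: "The physiotherapists will not have access to the results of the questionnaires completed by the patients prior to the initial consultation". Under data collection and management it says: "At the conclusion of the study all Webropol data will be transferred to Linköping University". The section on access to data limits study data to the research group and statistical support.

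**The concern.** An instrument that can register worsening protects nobody unless someone looks at the worse end of it. As planned, a patient whose pain rises is averaged into a mean, or placed in the same category as a patient who did not change. The study-specific MCID does not help, because its GRoC anchor separates improved from not improved and so yields a threshold for improvement only.

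The pattern at risk is a mixed response, in which some patients gain and others lose. Means and improved-or-not splits are poor at showing it. At stake is whether a null or favourable PROM result can be read as evidence that the film does not make some patients worse. That matters because the protocol foresees wider use, possibly national, if the results are positive.

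**Working it through.** The plan gives no figure for deterioration, so there is none to reproduce. The check has two parts.

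**1. Which planned PROM output separates worse from unchanged?**

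| Output | Worse side kept apart? |
|---|---|
| Mean change in NRS, PSEQ-10, BIPQ and other scores | No, averaged |
| GRoC, -5 to 0 against 1 to 5 | No, pooled with unchanged |
| Responder analysis at the MCID | No, pooled with unchanged and small improvement |

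No output gives the number worsened by arm.

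**2. Can these outputs hide a difference in worsening?**

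Input from the protocol: 408 patients, so 408/2 = 204 per arm. All rates and changes below are assumed, and GRoC category is assumed to line up with pain change.

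| | Worse | Unchanged | Improved |
|---|---|---|---|
| Control | 10% | 40% | 50% |
| Film | 20% | 22% | 58% |
| Average NRS change | +1.5 | 0 | -3 |

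- Mean change, control: 0.10 × 1.5 - 0.50 × 3 = -1.35.
- Mean change, film: 0.20 × 1.5 - 0.58 × 3 = -1.44.
- Difference: -1.44 - (-1.35) = -0.09, leaning towards the film.
- Odds ratio for improved: (0.58/0.42)/(0.50/0.50) = 1.38, leaning towards the film.
- Worse: 0.20 × 204 = about 41 against 0.10 × 204 = about 20 patients. The difference is 0.10, with SE = √(0.10 × 0.90/204 + 0.20 × 0.80/204) = 0.035. The 95% CI is 0.10 ± 1.96 × 0.035, about 3 to 17 points.

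Power to detect a difference in worsening if it were counted (two-sided 5%, normal approximation, 204 per arm): 81% for 10% v 20%, 48% for 5% v 10%, 33% for 10% v 15%.

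**Range.** Let w be the film arm's worsening rate and u the average rise in those who worsen. The means are equal when the film arm's improved share is 0.50 + (w - 0.10) × u/3. With u = 1.5 that is 52.5%, 55% or 57.5% for w = 15%, 20% or 25%. With w = 20%, it runs from 53.3% (u = 1) to 60% (u = 3). In every case the improved share exceeds the control arm's 50%, so the improved-or-not comparison favours the film.

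**Counter-check: harm on average.** With the protocol's planning SD of 4, the SE of a difference in means is 4 × √(2/204) = 0.396. The chance that the two-sided 95% CI lies wholly on the harm side is Φ(d/0.396 - 1.96):

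- d = 0.5 NRS points: 24%
- d = 1: 71%
- d = 2: over 99%

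**The case against.** The strongest reply is that the trial is less blind to harm than this sounds, and much of that stands.

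- **Reason for having no committee.** A reader might infer that the committee was waived because of the PROMs. The stated reasons are independence from the sponsor and low risk; the PROM sentence stands next to them but outside that clause.
- **Other signals.** A reader might infer that nothing in the results could show harm. That is too strong. Analgesic use, sick leave, healthcare visits, referrals and costs are compared by arm. Withdrawals are reported with reasons, and late-diagnosed serious pathology is named as a reason for exclusion. These signals are indirect, and none counts worsened patients.
- **Average and subgroup harm.** The counter-check shows that a general harmful shift would often be visible in the intervals, though the one-sided superiority test alone would only fail to show benefit. The moderator analysis by ÖMPSQ risk group could reveal a harmed subset, but only one that follows that split.
- **Timing and access.** A reader might infer that nobody sees data before the end, or that physiotherapists never learn of worsening. The interim analysis did compare arms at time points 2 and 3, though its only stopping rule concerned feasibility. The explicit no-access rule covers questionnaires completed before the consultation. Patients in both arms are asked there to reflect on those questionnaires and can speak up.
- **Realism.** The illustrative rates were chosen to show cancellation. The documents do not say that worsening is expected, and patients are triaged for suspected serious pathology before entry.

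None of this supplies a count of who got worse.

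**Conclusion.** The point holds in a limited form. The section on harms relies on a property of the PROMs that no planned analysis uses, so harm confined to a subset and offset by benefit elsewhere could be missed by the PROM analyses. In the illustration, a doubling of worsening from 10% to 20% coexists with a mean and an improvement rate that both lean towards the film.

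This rests on assumed distributions, on 204 analysable patients per arm, and on GRoC and pain moving together. The roughly 90% response that the protocol reports covers time points 2 and 3 only, so precision at three months may be lower. The documents do not support a claim that such masking is likely, or that a broad harmful effect would go unseen. The primary analysis is unaffected. This is a low-cost gap in safety reporting that should be closed before the data are analysed.

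**What to change.** 1. **SAP, global rating of change.** Report three levels by arm at time points 2, 3 and 4: worse (-5 to -1), unchanged (0), improved (1 to 5). Give the risk difference and 95% CI for worse. The planned two-level analysis can stay.
2. **SAP, responder analysis.** For the two primary outcomes use improved / unchanged / deteriorated. Keep the study-specific MCID for improved. Define deteriorated as an NRS rise of at least 2 (the protocol's cited MCID) and a PSEQ-10 fall of at least 11.52 (the cited minimal detectable change). The cited PSEQ-10 MCIDs of 5.5 to 8.5 lie below that detectable change, so a table built on them could count measurement error as harm. Show them only as a sensitivity display.
3. **Labelling.** Call these descriptive safety summaries, separate from the efficacy tests.
4. **Protocol, study monitoring and harms.** Reconcile the sentence on sensitivity to worsening with the passages on physiotherapists' access, data transfer and data access. State whether the PROMs are an end-of-trial safety outcome or ongoing monitoring and, if the latter, who sees them and when.

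The cost is SAP wording, one or two tables and one protocol sentence, with no new data. The downside is a few extra comparisons. Power is modest for small differences, so an interval that includes zero should not be read as proof of no harm.

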This statistical analysis plan is part of the PainSMART-project which is a collective suite of studies utilising mixed methods. The PainSMART-project was initiated in 2021 with the aim of improving early musculoskeletal pain (MSKP) management through patient-centered MSKP education based on modern pain science. The PainSMART project's motivation is the high burden of MSKP and the issues encountered within primary care clinical practice associated with the persistence of misconceptions surrounding MSKP. The PainSMART-project has to date conducted pilot-studies within the primary care setting that have led to the development of the seven-minute-long digital educational film entitled 'Be PainSMART:er' (hereafter known simply as 'the film'). The film forms the basis for the implementation of a two-stage PainSMART-strategy which consists of exposure to the film prior to the initial physiotherapy consultation and a discussion based on the film between the patient and the physiotherapist at the initial physiotherapy consultation. The aim of this study is to scientifically evaluate the effects of adding the PainSMART-strategy to the current MSKP primary care physiotherapy care pathway in the Swedish healthcare regions of Östergötland (RÖ) and Jönköping (RJL).

Description of specific objectives or hypotheses

The objective of the PainSMART-project is to evaluate the effects of administering the PainSMART-strategy as an adjunct to usual physiotherapy management compared to usual physiotherapy management alone.

Research hypotheses for confirmatory research questions

1. Exposure to the PainSMART-strategy as an adjunct to usual physiotherapy management improves the following outcomes significantly more than usual physiotherapy management alone for patients with MSKP (* = primary outcomes) (H1)

- Reduction in pain intensity*.
- Higher pain self-efficacy*.
- Lower MSKP illness perceptions.
- Higher levels of reassurance of the benign nature of MSKP.
- More adaptive MSKP coping and psychological flexibility.
- Higher self-reported levels of physical activity.
- More positive global ratings of change.
- Lower number of healthcare visits, referrals for diagnostic imaging and to specialist/tertiary care for MSKP, lower analgesic medication use, fewer sick leave days and lower direct costs.
- More positive and concordant patient and physiotherapist evaluations of MSKP-related shared understanding, communication, participation, involvement and emotional support at the initial physiotherapy consultation.

2. Improvements in MSKP illness perceptions and higher levels of reassurance of the benign nature of MSKP mediate improved pain intensity and pain self-efficacy as a result of exposure to the PainSMART-strategy compared to usual physiotherapy management alone.

The null hypothesis (H0) is that there is no clinically or statistically significant differences between the intervention (film) group and the control group (usual physiotherapy management).

Secondary exploratory research questions

1. What baseline factors are predictive of improved patient outcomes after exposure to the PainSMART-strategy?
2. What baseline factors are predictive of the persistence of MSKP?
3. What type of psychological factors and strategies are associated with patient outcomes after exposure to the PainSMART-strategy?
4. Is pain self-efficacy a potential mediator of the PainSMART-strategy's effect on health outcomes?
5. What are patients and physiotherapists experiences of the PainSMART-strategy?

Study Methods

Trial design

This is a two-armed, parallel group, randomised controlled trial in which the intervention group (PainSMART-strategy + usual physiotherapy management) will be compared to a control group (usual physiotherapy management). Treatment allocation is a 1:1 ratio. The control group and statistician will be blinded. One independent statistician will be blinded for the primary analyses. Another independent statistician will be responsible for database development and linkage of patient and physiotherapist data. The PainSMART-strategy is described in full in the trial protocol.

Randomisation

A computerised randomisation sequence for 800 patients into group A (Intervention group) or B (Control group) has been generated by a blinded statistician using SPSS prior to the start of patient recruitment. Participating patients will be allocated to intervention or control group based on the order of their inception to the study. The randomisation is described in full in the trial protocol.

Framework

The trial's hypotheses apply a superiority testing framework where the PainSMART-strategy is hypothesized to be superior in outcome compared to control.

Determination of Sample size

The sample size calculation is described in full in the trial protocol.

Adherence and protocol deviations

The definition of adherence in the intervention group is viewing of the film and receiving the structured PainSMART-questions at the initial physiotherapy consultation. Adherence to viewing of the film will be assessed through the obligatory patient reported experience measure (PREMs) questions directly after the film and patient-reported number of times viewing the film. Receiving the structured PainSMART-questions will be assessed by physiotherapists' self-reported adherence to the study protocol. The definition of adherence in the control group is receiving one question from the physiotherapist concerning the

questionnaires that the patient had filled in prior to the initial consultation. This will be assessed by physiotherapists' self-reported adherence to the study protocol.

Adherence in the intervention group will be presented as descriptive statistics (number and percentage) related to the patients' self-reporting of the number of viewings of the film (out of a maximum of two) as well as physiotherapist reported adherence to the structured PainSMART-questions at the initial physiotherapy consultation. Adherence in the control group will be presented with descriptive statistics regarding the number and percentage of patients who have received the question regarding the questionnaires at first consultation. Patients that deviate from protocol are those that, despite randomisation to the intervention group, have not answered the PREMs questions following initial exposure to the film and/or those who have reported not viewing the film at either data collection time points 1 or 2. Patients deviating from protocol are also those patients in the intervention and control groups who have not received the structured questions according to protocol, as reported by the treating physiotherapist. The number of patients deviating from the protocol will be summarised in each allocation group with details of type of deviation provided.

Minor deviation

- No exposure to the structured PainSMART-questions (intervention group)
 - * or question regarding the questionnaires at first consultation (control group)[#]
 - * In case of exposure to the film and actively cancelled physiotherapy consultation
 - # In case of exposure to baseline questionnaires and actively cancelled physiotherapy consultation

Major deviation

- No exposure to the film and the PainSMART-questions (Intervention group)

Statistical analysis population

The analysis populations include an intention-to-treat population (ITT) and a per-protocol population for this trial. The ITT population will include all randomised patients according to the treatment they were randomised to receive. ITT is the primary efficacy analysis population for this study. A per-protocol population will be considered for participants who received the intervention protocol with no or minor deviation from the protocol.

[Trial Population](#)

[Screening data](#)

The total number of eligible participants could not be collected during the study as it was considered too resource intensive and would not be sufficiently reliable. Register data on numbers of first physiotherapy consultations for MSKP at the rehabilitation units during the study recruitment period will be collected. Demographic and baseline characteristics (see "Demography and baseline characteristics") will be collected to enable analysis of the representativeness of the study sample (patient participants).

The following demographic data will be collected and presented to enable analysis of the representativeness of the sample of participating physiotherapists: employer, age, sex, level of education, number of years working as a physiotherapist.

Eligibility

The inclusion and exclusion criteria are reported in the protocol. In the case that participants have initially fulfilled these criteria and been randomly allocated to a group but at a later time point have been found to not fulfil the criteria (e.g. the late diagnosis of a serious medical condition), the number of ineligible patients randomised, if any, will then be reported with reasons for ineligibility.

Recruitment

A CONSORT flow diagram will be used to summarize the number of patients who were:

- Eligible for screening
- Ineligible at screening
- Eligible at screening but not randomised - Declined to participate (n=....)
- Randomised (n=...)
- Number excluded post randomisation (n=...) *Reasons ex. consent withdrawal, late diagnosed serious pathology
- Allocated to intervention (n=...)
 - Received allocated intervention (n=...)
 - No exposure to the film and the PainSMART-questions (major deviation) (n=...)
 - No exposure to the PainSMART-questions (minor deviation) (n=...)*
 - *Reason: Physiotherapist adherence to protocol (n=...); Cancelled physiotherapy consultation (n=...)
 - Exposure to the whole PainSMART-strategy (n=....)
 - Did not receive allocated intervention, plus reasons (n=...)
- Allocated to control (n=...)
 - Received allocated intervention (n=...)
 - No exposure to the PainSMART-question (minor deviation) (n=...)
 - *Reason: Physiotherapist adherence to protocol (n=...); Cancelled physiotherapy consultation (n=...)
- Lost to follow-up
 - Lost to follow-up intervention group
 - PROM + PREM outcomes
 - Time point 1 (n=...)
 - Time point 2 (n=...)
 - Time point 3 - Primary time point one (n=...)
 - Time point 4 - Primary time point two (n=...)
 - Physiotherapists - PREM
 - Lost to follow-up control group
 - PROM + PREM outcomes
 - Time point 1 (n=...)
 - Time point 2 (n=...)
 - Time point 3 - Primary time point one (n=...)
 - Time point 4 - Primary time point two (n=...)

Physiotherapists – PREM

- Analysed (n=...)
 - Analysed intervention group PROMs
 - Time point 1 (n=...)
 - Time point 2 (n=...)
 - Time point 3 - Primary time point one (n=...)
 - Time point 4 - Primary time point two (n=...)
 - Analysed intervention health register outcomes (n=...)
 - Analysed intervention PREM outcomes (n=...)
 - Analysed control group PROMs
 - Time point 1 (n=...)
 - Time point 2 (n=...)
 - Time point 3 - Primary time point one (n=...)
 - Time point 4 - Primary time point two (n=...)
 - Analysed control health register outcomes (n=...)
 - Analysed control PREM outcomes (n=...)

Participant drop-out

The number of patients and physiotherapists actively withdrawing from the trial will be reported, with reasons where available. Consent withdrawal will be classified as “complete – no further follow-up or data collection”. Lost to follow-up will be classified as “non-response at follow-up”. Timing of withdrawal and lost to follow-up will be presented in CONSORT diagram format, and if needed a table, with numbers and reasons for withdrawal, lost to follow-up and exclusion from analysis given at each stage (intervention delivery, prior to the initial physiotherapy consultation, post physiotherapy consultation, three months post baseline). Details on reasons for withdrawal will be presented descriptively.

Demography and baseline characteristics

Patients will be described with respect to demographical factors and baseline characteristics listed below, separately for the two randomised groups.

- Age
- Sex
- Level of education
- Employment including current sickness certification/leave for present MSKP complaint
- Pain duration
- Pain location for actual presenting complaint
- Number of other MSKP sites
- Body mass index (BMI)
- Previous healthcare interventions for the actual presenting complaint in the last three months
- Previous healthcare interventions for other MSKP sites in the last three months

- Analgesic medication use (type and consumption)
- Number of comorbidities
- Risk for future work-related disability – low or high risk according to score on Örebro musculoskeletal pain screening questionnaire (ÖMPSQ), where >50 is classified as high-risk.
- Average waiting time to initial physiotherapy consultation

Baseline PROM scores

- Pain intensity with numerical rating scales (NRS).
 - o Worst pain in the last 24 hours (0-10).
 - o Best pain in the last 24 hours (0-10).
 - o Average pain in the last 24 hours (0-10).
- Pain self-efficacy - Pain self-efficacy questionnaire (PSEQ-10; max score 60).
- Traditional pain coping - Brief Pain Coping Inventory (BPCI-2) traditional pain coping subscale (max score 56).
- Psychological flexibility in pain - BPCI-2 psychological flexibility subscale (max score 49).
- MSKP illness perceptions - Brief Illness Perception Questionnaire (BIPQ; max score 80).
- Level of concern as to the potential likelihood of MSKP being caused by a serious pathology - Single question rated on a NRS (0-10).
- Self-reported physical activity in the past week based on three questions
 - o Moderate to intensive exercise (minutes)
 - o Other physical activity beside exercise (minutes)
 - o Sitting time (minutes during a regular day)

Physiotherapists will be described with respect to age, sex, level of education and number of years working as a physiotherapist. Data will be presented for the whole cohort of physiotherapists and separately for the physiotherapists providing treatment in the two randomised groups.

Normally distributed continuous data will be summarised by mean, standard deviations (SD). For non-normally distributed continuous data, median and lower, upper quartile range, will be provided unless otherwise stated. Categorical data will be summarised by number and percentages. Tests of statistical significance will be undertaken for screening of imbalance between groups in baseline characteristics.

Analysis

Time frame for data collection

Primary and secondary patient reported outcome measures (PROMs) will be collected at four time points:

1. Baseline: the same day as initial triage.
2. 24 -72 hours prior to the initial physiotherapy consultation.
3. 24 hours post the initial physiotherapy consultation (primary time point one).
4. Three months post-baseline (primary time point two).

In addition, patients' reported experiences of the film and PROMs will be collected directly after exposure to the film in the intervention group. Secondary physiotherapist and patient reported experience measures (PREM) will be collected at time point 3. Healthcare register data relating to the three month study period for each participating patient will be collected after the completion of PROMs and PREMs data collection for all participants.

Data on the physiotherapists' adherence to the Pain-SMART strategy will be collected after all the first 450 included participants have had their first physiotherapy consultations (after time point three) approximately eight months after the inclusion of the first participant and prior to the start of patient inclusion to the qualitative phase of the trial. For primary and secondary PROM data the primary time points are defined as 24 hours post initial physiotherapy consultation (primary time point one) and three months post-baseline (primary time point two). The data collection is described in full in the trial protocol.

Outcome definitions

The primary and secondary outcomes are described in full in the trial protocol. Both trial arms have the following outcomes measured:

Primary outcomes

- Pain intensity

Self-reported average pain intensity in the previous 24 hours will be measured using numerical rating scales (NRS). Score range: 0-10 with 0 = no pain and 10 = worst imaginable pain.

- Time Frame: collected at baseline, 24 hours post initial physiotherapy consultation and at three months post-baseline.
- Calculation to derive outcome:
 - Between group mean change over time from baseline to 24 hours post initial physiotherapy consultation (primary time point one)
 - Between group mean change over time from baseline to three months post-baseline (primary time point two)

-Pain self-efficacy

Self-reported pain self-efficacy will be measured using the Pain Self-efficacy Questionnaire 10 (PSEQ-10). The PSEQ-10 is a 10-item questionnaire. Score range: 0-60, a higher score indicating greater pain self-efficacy.

- Time Frame: collected at baseline, 24 hours post initial physiotherapy consultation and at three months post-baseline.

- Calculation to derive outcome:
 - Between group mean change over time from baseline to 24 hours post initial physiotherapy consultation (primary time point one)
